14 ETHICAL CONSIDERATIONS

This study will be conducted according to the standards of International Council on Harmonization, Good Clinical Practice Guideline, Research Ethics Committee regulations, any applicable government regulations, Trust and Research Office policies and procedures.

This protocol, the ICF, relevant supporting information, and all types of subject recruitment or advertisement information must be submitted to the IRB/Ethics Committee for review and must be approved before the study is initiated. Any amendments to the protocol must also be approved by the IRB/Ethics Committee prior to implementing changes in the study. The investigator is responsible for

keeping the IRB/Ethics Committee apprised of the progress of the study, any SAEs, and any changes made to the protocol according to the requirements of the site's IRB.

Appendix 1Time and Events Schedule

See Section 8.3 for order of assessments.

Study Parameter*	Screening/ Baseline Visi Day -14	t Insertion Day Day 1	Follow- up Week 2 ±2 days	Follow-up Week 4 ±2 days	Follow-up Week 6 ±3 days	Follow-up Week 9 ±3 days	Follow-up Week 12 ±3 days	Final Visit Week 16 ⁸ ±3 days	30-Day Follow-Up Visit ⁹ (± 10 days)
Visit	1	2	3	4	5	6	7	8	9
Informed Consent	X								
Determine Eligibility	Х	Х							
Demographic Information	Х								
Medical/Ophthalmic History	Х								
Record Medications	Х	Х	Х	Х	X	Х	X	Х	Х
Record Adverse Events ¹⁰		Х	Х	Х	X	Х	Х	Х	Х
Urine Pregnancy Test ¹	Х							Х	
OSDI	X	Х	Х	Х	X	X	X	Х	Х
VAS for Eye Dryness	X	Х	Х	Х	X	X	X	Х	Х
SPEED	X	Х	Х	Х	X	X	X	Х	Х
Corneal Fluorescein Staining Using the NEI Scale	X	Х	X	Х	Х	Х	Х	Х	X
Conjunctival Lissamine Green Staining Using the NEI Scale	Х	Х	X	Х	Х	Х	Х	Х	X
Assessment of BCVA	Х	Х	Х	Х	X	Х	X	X	Х
Slit Lamp Biomicroscopy (including punctum assessment)	Х	X^4	X	Х	Х	Х	Х	Х	X
OTX-CSI or HV Insert Presence by Visual Assessment			Х	Х	Х	Х	Х	Х	X
Ease of Visualization as assessed by Investigator			Х	Х	Х	Х	Х	Х	Х
Systemic PK sample collection ² (at selected sites)		X ⁵	X						
Tear Film PK sample collection ⁷ (at all sites)		X ⁶	X	Х	X	X	X	X	X
Measurement of TBUT	Х	Х			Х		Х		
Schirmer Test (without anesthesia)	X	Х	X	Х	Х	Х	Х	Х	Х
IOP Measurement	Х	Х						Х	
Fundus Exam ³	Х							Х	

Study Parameter*	Screening/ Baseline Visit Day -14	Insertion Day Day 1	Follow- up Week 2 ±2 days	Follow-up Week 4 ±2 days	Follow-up Week 6 ±3 days	Follow-up Week 9 ±3 days	Follow-up Week 12 ±3 days	Final Visit Week 16 ⁸ ±3 days	30-Day Follow-Up Visit ⁹ (± 10 days)
Visit	1	2	3	4	5	6	7	8	9
Punctum Size Assessment		Х						Х	
Randomization (Cohort 2)		Х							
OTX-CSI or HV Insert Placement		X ^{11 & 12}							
Ease of Insertion as assessed by the Investigator		Х							
Dispense Artificial Tears (as needed)	Х	Х	х	Х	Х	Х	Х	Х	Х
Dispense Daily Subject Diary for Artificial Tear Use (as needed)	X	X	Х	Х	Х	Х	X	X	X
Collect/review Daily Subject Diary for Artificial Tear Use (as needed)		X	X	Х	Х	Х	Х	Х	Х

*All examinations need to be performed on both eyes. See Section 8.4 to confirm the order that the assessments should be performed.

1 A negative UPT is required for women of childbearing potential to be included in the study.

- 2 Select sites will collect Systemic PK. All sites will collect Tear Film PK.
- 3 Dilated fundus examination at screening; undilated fundus examination at Week 16.
- 4 Prior to insertion, a clinical determination of the absence of infection will be made based on the lack of erythema or discharge at the punctum.
- 5 Systemic PK sample on Day 1 will be collected after successful insertion at 2 hours (±30 minutes) or 4 hours (±30 minutes) post-insertion.
- 6 Tear Film PK will be collected at 1 hour (±30 minutes), 2 hours (±30 minutes), and 4 hours (±30 minutes) post insertion on Day1. Tear Film PK should be collected using Schirmer strips.
- 7 Tear Film PK will be collected using Schirmer Tests strips. These will be collected and sent to the central lab for analysis. See lab manual.
- 8 Early termination subjects should complete assessments based on the final visit (Visit 8) schedule of assessments.
- 9 Post week 16 visit will be conducted every 30 days (± 10 days) until an insert can no longer be visualized and the physician has determined that there is no evidence of biological activity. Additionally, subjects may be exited at the investigator's discretion.
- 10 Signs, symptoms, conditions occurring prior to insertion on Day 1 should be captured as medical history.
- 11 For Cohort 1 subjects only, within the first six weeks post treatment, if an insert is not visualized in one or both eyes by the Investigator, the Investigator should place a new insert in the respective eye(s) after confirming patency. Refer to Appendix 13 for placement instructions. Replacement of inserts for Cohort 2 subjects is not permitted.

12 If placement is only successful in one eye, subjects should be asked to return within 1-3 days to attempt insertion in the other eye. The following items should be repeated at the return visit, Insert Placement, Ease of Insertion, Tear Film PK and AEs.

Appendix 2 Safety Review Group Charter

The recommendation to continue into Cohort 2 (double-masked, vehicle-controlled, portion of the study) will be the responsibility of a Safety Review Group constituted by the Principal Investigator(s) of the study, the Medical Monitor and the Chief Medical Officer at Ocular Therapeutix, Inc. The SRG, may request the participation of an independent statistician and/or independent medical expert to assist in the assessment of the safety of the IP and the recommendation to progress.

In order to maintain the integrity of the trial, unless it is absolutely necessary, the safety review should be conducted using masked subjectspecific information. The Safety Review Group will convene after all subjects in Cohort 1 have been followed for at least 2 weeks (or at any time during the study if necessary) to evaluate the safety of the IP. Upon review and evaluation, the SRG will issue a recommendation to Ocular Therapeutix, Inc.

General guidelines for the recommendation to escalate to the next cohort:

A recommendation to escalate to the next cohort may be issued if no more than 1 dose limiting toxicity (DLT) is found during or at the end of the cohort.

Indicators of DLT in this study will be assessed according to the Common Terminology Criteria for Adverse Events (CTCAE) (version 5.0, Published November 27, 2017).

A DLT is defined as one of the following events at the specified toxicity level deemed by the Investigator to be related to OTX-CSI and based on CTCAE (version 5.0)¹

- Any Grade 3 or higher adverse event
- Any Grade 2 or higher adverse event that in the judgment of the Investigator or Sponsor requires discontinuation of dosing
- Any Grade 2 or higher adverse event that in the judgment of the Investigator or Sponsor requires further investigation before determining dose escalation.

Events, including serious adverse events (SAEs), deemed by the Investigator to be related to the subject's underlying medical condition, will not be considered DLTs and used for determination of dose escalation, e.g., hyperglycemic event.

¹ Grade refers to the severity of the AE. The CTCAE displays Grades 1 through 5 with unique clinical descriptions of severity for each AE based on this general guideline: Grade 1 Mild; asymptomatic or mild symptoms; clinical or diagnostic observations only; intervention not indicated. Grade 2 Moderate; minimal, local or noninvasive intervention indicated; limiting age-appropriate instrumental ADL. Grade 3 Severe or medically significant but not immediately life-threatening; hospitalization or prolongation of hospitalization indicated; disabling; limiting self care ADL. Grade 4 Life-threatening consequences; urgent intervention indicated. Grade 5 Death related to AE.

Recommendations:

The recommendations of the Safety Review Group to Ocular Therapeutix, Inc. may include:

- Escalate to Cohort 2
- Repeat Cohort 1
- Amend the protocol
- Stop the study

If the safety data obtained in Cohort 1 warrants continuation of the study and initiation of Cohort 2, the Safety Review Group will issue a memorandum to Ocular Therapeutix, Inc. recommending continuing to Cohort 2.

If a review of Cohort 2 data is required and upon the review of the masked safety information, the Safety Review Group requires unmasked information in order to ensure the safeguard of the interests of the study subjects, the unmasked information will be provided. Please refer to Section 10.9.2 for unmasking procedures.

The Safety Review Group will make every effort to arrive to a recommendation by consensus.

Ocular Therapeutix, Inc. representatives then will make a decision that is consistent primarily with the safeguard of the interests of the study subjects.

	Eye disorders								
CTCAE Term	Grade 1	Grade 2	Grade 3	Grade 4	Grade 5				
Blurred vision Definition: A disorder characteri Navigational Note: -	Intervention not indicated zed by visual perception of unclear	Symptomatic; moderate decrease in visual acuity (best corrected visual acuity 20/40 and better or 3 lines or less decreased vision from known baseline); limiting instrumental ADL or fuzzy images.	Symptomatic with marked decrease in visual acuity (best corrected visual acuity worse than 20/40 or more than 3 lines of decreased vision from known baseline, up to 20/200); limiting self care ADL	Best corrected visual acuity of 20/200 or worse in the affected eye	-				
Cataract	Asymptomatic; clinical or diagnostic observations only; intervention not indicated	Symptomatic; moderate decrease in visual acuity (best corrected visual acuity 20/40 and better or 3 lines or less decreased vision from known baseline); glare symptoms affecting instrumental ADL	Symptomatic with marked decrease in visual acuity (best corrected visual acuity worse than 20/40 or more than 3 lines of decreased vision from known baseline, up to 20/200); limiting self care ADL	Best corrected visual acuity of 20/200 or worse in the affected eye	-				
Definition: A disorder characteri untreated. Navigational Note: -	zed by partial or complete opacity o	of the crystalline lens of one or both	eyes. This results in a decrease in	visual acuity and eventual blindnes:	if				
Corneal ulcer Definition: A disorder characteri	- zed by an area of epithelial tissue lo	- oss on the surface of the cornea. It is	Corneal ulcer without perforation in the affected eye s associated with inflammatory cell	Perforation in the affected eye s in the cornea and anterior chamb	- er.				
Navigational Note: -									
Dry eye	Asymptomatic; clinical or diagnostic observations only; symptoms relieved by lubricants	Symptomatic; moderate decrease in visual acuity (best corrected visual acuity 20/40 and better or 3 lines or less decreased vision from known baseline)	Symptomatic with marked decrease in visual acuity (best corrected visual acuity worse than 20/40 or more than 3 lines of decreased vision from known baseline, up to 20/200); limiting self care ADL	-	-				
Definition: A disorder characteri	zed by dryness of the cornea and co	onjunctiva.							
Navigational Note: If corneal uld	er is present, grade under Eye disor	rders: Corneal ulcer.							

		Eye disorders			
CTCAE Term	Grade 1	Grade 2	Grade 3	Grade 4	Grade 5
Extraocular muscle paresis	Asymptomatic; clinical or diagnostic observations only	Unilateral paresis without double vision	Bilateral paresis or unilateral paresis causing double vision in peripheral gaze, but not in central gaze	Bilateral paresis requiring head turning to see beyond central 60 degrees or double vision in central gaze	-
Definition: A disorder characteriz	zed by incomplete paralysis of an e	xtraocular muscle.			
Navigational Note: -					
Eye pain	Mild pain	Moderate pain; limiting instrumental ADL	Severe pain; limiting self care ADL	-	-
Definition: A disorder characteriz	zed by a sensation of marked disco	mfort in the eye.			
Navigational Note: -				1	·
Eyelid function disorder	Asymptomatic; clinical or diagnostic observations only; intervention not indicated	Symptomatic; nonoperative intervention indicated; limiting instrumental ADL	Limiting self care ADL; operative intervention indicated	-	-
Definition: A disorder characteriz	zed by impaired eyelid function.		I	I	1
Navigational Note: -	, , ,				
Flashing lights	Symptomatic but not limiting ADL	Limiting instrumental ADL	Limiting self care ADL	-	-
Definition: A disorder characteriz	zed by a sudden or brief burst of lig	ht.			
Navigational Note: Also consider	Eye disorders: Retinal tear or Retin	nal detachment			
Floaters	Symptomatic but not limiting ADL	Limiting instrumental ADL	Limiting self care ADL	-	-
Definition: A disorder characteriz	zed by an individual seeing spots be	fore their eyes. The spots are shad	ows of opaque cell fragments in th	e vitreous humor or lens.	
Navigational Note: Also consider	r Eye disorders: Retinal tear or Reti	nal detachment			
Glaucoma	Less than 8 mmHg of elevated	EIOP which can be reduced to	EIOP causing visual field	Visual field deficit within the	-
	intraocular pressure (EIOP);	21 mmHg or under with	deficits	central 10 degrees of the	
	no visual field deficit	topical medications and no		visual field in the affected eye	
Definition: A disorder characteriz	I zed by an increase in pressure in th	e eveball due to obstruction of the	aqueous humor outflow.	1	I
Navigational Note: -			adarren unun ontioni		

	Eye disorders								
CTCAE Term	Grade 1	Grade 2	Grade 3	Grade 4	Grade 5				
Keratitis	Asymptomatic; clinical or diagnostic observations only; intervention not indicated	Symptomatic; moderate decrease in visual acuity (best corrected visual acuity 20/40 and better or 3 lines or less decreased vision from known baseline)	Symptomatic with marked decrease in visual acuity (best corrected visual acuity worse than 20/40 or more than 3 lines of decreased vision from known baseline, up to 20/200); corneal ulcer; limiting self care ADL	Perforation; best corrected visual acuity of 20/200 or worse in the affected eye	-				
Navigational Note: Also consider	Evo disordors: Corpoal ulcor	of the eye.							
Night blindness	Symptomatic but not limiting ADL	Symptomatic; moderate decrease in visual acuity (best corrected visual acuity 20/40 and better or 3 lines or less decreased vision from known baseline); limiting instrumental ADL	Symptomatic with marked decrease in visual acuity (best corrected visual acuity worse than 20/40 or more than 3 lines of decreased vision from known baseline, up to 20/200); limiting self care ADL	Best corrected visual acuity of 20/200 or worse in the affected eye	-				
Definition: A disorder characteri	ı zed by an inability to see clearly in (dim light.		I	I				
Navigational Note: -		0							
Optic nerve disorder	Asymptomatic; clinical or diagnostic observations only	Moderate decrease in visual acuity (best corrected visual acuity 20/40 and better or 3 lines or less decreased vision from known baseline)	Marked decrease in visual acuity (best corrected visual acuity worse than 20/40 or more than 3 lines of decreased vision from known baseline, up to 20/200)	Best corrected visual acuity of 20/200 or worse in the affected eye	-				
Definition: A disorder characteri	zed by involvement of the optic ner	ve (second cranial nerve).							
Navigational Note: -									
Papilledema	Asymptomatic; no visual field deficit	Symptomatic; moderate decrease in visual acuity (best corrected visual acuity 20/40 and better or 3 lines or less decreased vision from known baseline)	Symptomatic with marked decrease in visual acuity (best corrected visual acuity worse than 20/40 or more than 3 lines of decreased vision from known baseline, up to 20/200)	Best corrected visual acuity of 20/200 or worse in the affected eye	-				
Definition: A disorder characteri	zed by swelling around the optic di	5C.							
Navigational Note: -									

Eye disorders								
CTCAE Term	Grade 1	Grade 2	Grade 3	Grade 4	Grade 5			
Periorbital edema	Soft or non-pitting	Indurated or pitting edema;	Edema associated with visual	-	-			
		topical intervention indicated	disturbance; increased					
			intraocular pressure,					
			glaucoma or retinal					
			hemorrhage; optic neuritis;					
			diuretics indicated; operative					
			intervention indicated					
Definition: A disorder characteri	zed by swelling due to an excessive	accumulation of fluid around the o	rbits of the face.					
Navigational Note: -		· · ·			r			
Photophobia	Symptomatic but not limiting	Limiting instrumental ADL	Limiting self care ADL	-	-			
	ADL							
Definition: A disorder characteri	zed by fear and avoidance of light.							
Navigational Note: -	1 .	1 · · ·	· · · · ·	1				
Retinal detachment	-	-	Macular sparing	Macula-off rhegmatogenous	-			
			rhegmatogenous detachment	retinal detachment				
Definition: A disorder characteri	zed by the separation of the inner r	etina layers from the underlying pi	gment epithelium.					
Navigational Note: -	+ · · ·	· · · ·	،					
Retinal tear	No retinal detachment and	No retinal detachment and	-	-	-			
	treatment not indicated	treatment indicated						
Definition: A disorder characteri	zed by a small laceration of the reti	na, this occurs when the vitreous se	eparates from the retina. Symptom	s include flashes and floaters.				
Navigational Note: If retinal deta	achment is present, grade under Ey	e disorders: Retinal detachment						
Retinal vascular disorder	-	Retinal vascular disorder	Retinal vascular disorder with	-	-			
		without neovascularization	neovascularization					
Definition: A disorder characteri	zed by pathological retinal blood ve	essels that adversely affects vision.						
Navigational Note: If vitreous he	morrhage is present, report under	Eye disorders: Vitreous hemorrhage	e.					
Retinopathy	Asymptomatic; clinical or	Symptomatic; moderate	Symptomatic with marked	Best corrected visual acuity of	-			
	diagnostic observations only	decrease in visual acuity (best	decrease in visual acuity (best	20/200 or worse in the				
		corrected visual acuity 20/40	corrected visual acuity worse	affected eye				
		and better or 3 lines or less	than 20/40 or more than 3					
		decreased vision from known	lines of decreased vision from					
		baseline); limiting	known baseline, up to					
		instrumental ADL	20/200); limiting self care ADL					
Definition: A disorder involving t	he retina.							
Navigational Note: If vitreous he	morrhage is present, report under	Eye disorders: Vitreous hemorrhage	е.					

	Eye disorders								
CTCAE Term	Grade 1	Grade 2	Grade 3	Grade 4	Grade 5				
Scleral disorder Definition: A disorder characteri Navigational Note: -	No change in vision from baseline zed by involvement of the sclera of	Symptomatic; moderate decrease in visual acuity (best corrected visual acuity 20/40 and better or 3 lines or less decreased vision from known baseline); limiting instrumental ADL the eye.	Symptomatic with marked decrease in visual acuity (best corrected visual acuity worse than 20/40 or more than 3 lines of decreased vision from known baseline, up to 20/200); limiting self care ADL	Best corrected visual acuity of 20/200 or worse in the affected eye	-				
Uveitis Definition: A disorder characteri Navigational Note: -	Anterior uveitis with trace cells zed by inflammation to the uvea of	Anterior uveitis with 1+ or 2+ cells the eye.	Anterior uveitis with 3+ or greater cells; intermediate posterior or pan-uveitis	Best corrected visual acuity of 20/200 or worse in the affected eye	-				
Vision decreased	-	Moderate decrease in visual acuity (best corrected visual acuity 20/40 and better or 3 lines or less decreased vision from known baseline)	Marked decrease in visual acuity (best corrected visual acuity worse than 20/40 or more than 3 lines of decreased vision from known baseline, up to 20/200)	Best corrected visual acuity of 20/200 or worse in the affected eye	-				
Definition: A disorder characteri	zed by a decrease in visual acuity.								
Vitreous hemorrhage	Intervention not indicated	Symptomatic; moderate decrease in visual acuity (best corrected visual acuity 20/40 and better or 3 lines or less decreased vision from known baseline); limiting instrumental ADL	Symptomatic with marked decrease in visual acuity (best corrected visual acuity worse than 20/40 or more than 3 lines of decreased vision from known baseline, up to 20/200); limiting self care ADL; vitrectomy indicated	Best corrected visual acuity of 20/200 or worse in the affected eye	-				
Definition: A disorder characteri	zed by bleeding into the vitreous hu	umor.							
Navigational Note: -									

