6.3 Randomization and Blinding

Cohort 1 will be open-label and treatment assignment will be known to the sponsor, investigator and subjects. All 5 enrolled subjects in Cohort 1 will receive OTX-CSI Formulation 2A.

Cohort 2 will be randomized to treatment assignment and double-masked. If unmasking is required, the integrity of the study assessments and objectives will be maintained by limiting access to the unmasked data to the two individuals in the Safety Review Group (Sponsor Medical Monitor and Sponsor Statistician) who are not involved in the study conduct or directly by the investigator if required in an emergency.

A randomization schedule will be computer-generated by a qualified biostatistician independent of the study conduct or project team and uploaded into the EDC system. The EDC/IRT system will be used for randomization and unmasking.

The HV and OTX-CSI inserts administered to subjects at randomization in the double-masked treatment phase will be comparable in appearance. Study subjects and investigators and their staff will be masked to the identity of treatment until the final database is locked. The Sponsor's personnel involved with the conduct and monitoring of the study will remain masked until completion of the study and database lock.

Appropriate precautions must be taken to prevent unauthorized access to the randomization scheme. Unless the subject's safety requires otherwise and if time permits, the decision to unmask a treatment assignment is to be made jointly by the Investigator and Sponsor's medical monitor.

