10.9.2 Unmasking for Medical Emergencies

In the case of a medical emergency or occurrence of an SAE, the randomization code may be unmasked and made available to the Investigator, Sponsor, and/or other study personnel involved in the conduct of

the study. In the absence of medical need, the randomization code will not be available to the above individuals until after the study is completed and the database is locked.

In the event of a medical need, the Investigator will treat each subject, as medically required. If the Investigator feels it is necessary to unmask a subject's treatment assignment after an emergency situation, the Investigator may call the Medical Monitor and notify the Sponsor. The treatment assignment will be revealed on a subject-by-subject basis with the approval of the Medical Monitor and Sponsor, thus leaving the masking of the remaining subjects intact. Ocular Therapeutix will make the final determination if the unmasking request will be granted. Once the unmasking request is granted the investigator or designee should use the IRT system to unmask the subject's randomization code. The investigator must also indicate in source documents and in the eCRF that the mask was broken and provide the date, time, and reason for breaking the mask. Any AE or SAE associated with breaking the mask must be recorded and reported as specified in this protocol.

Subjects will have the IP removed (Appendix 15) immediately if treatment assignment is unmasked.

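### The Safety Review Group charter sends requests for unmasked Cohort 2 data to an emergency code-break procedure that ends in insert removal

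*Protocol*

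**What the plan says.** Protocol Appendix 2 makes masked review the SRG's default. It then allows a further step in Cohort 2: if the SRG, having seen the masked data, "requires unmasked information in order to ensure the safeguard of the interests of the study subjects, the unmasked information will be provided". The only procedure given is "Please refer to Section 10.9.2 for unmasking procedures".

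Section 10.9.2 is headed as a procedure for medical emergencies. It opens: "In the case of a medical emergency or occurrence of an SAE, the randomization code may be unmasked". It adds a limit: "In the absence of medical need, the randomization code will not be available to the above individuals" until the study is over and the database locked. Those individuals are the Investigator, the Sponsor and others who conduct the study. Assignments are released one subject at a time with Medical Monitor and Sponsor approval, and the Sponsor has the last word. Once a request is granted, "the investigator or designee should use the IRT system to unmask" the assignment. The section ends: "Subjects will have the IP removed (Appendix 15) immediately if treatment assignment is unmasked".

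Section 6.3 sets the access rule. When unmasking is needed, integrity is protected by "limiting access to the unmasked data to the two individuals in the Safety Review Group (Sponsor Medical Monitor and Sponsor Statistician"), neither of whom takes part in study conduct; the investigator may also unmask directly in an emergency. The same section states: "Study subjects and investigators and their staff will be masked to the identity of treatment until the final database is locked". It also makes the decision to unmask a joint one between the Investigator and the Sponsor's medical monitor, where safety and time allow. SAP Section 2.4 repeats the access rule and the joint decision. Section 8.3.11 rules out insert replacement in Cohort 2.

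**The concern.** An SRG request and an emergency code break serve different purposes. In an emergency, an investigator needs one assignment to manage one patient, and ending exposure at the same moment is reasonable. An SRG asks whether a safety pattern is linked to treatment. To answer that, someone outside study conduct may need the assignments of several subjects, many of them well, while the sites stay masked. Section 10.9.2 makes no provision for this, and its removal rule makes no exception for it.

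Two things are at stake:

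- **Treatment.** Cohort 2 subjects are treated once, with inserts placed on both sides. Removal ends study treatment, and Appendix 15 shows that removal is itself a procedure (manual expression, or dilation and saline irrigation).
- **Masking.** Investigators score the ophthalmic observations (Section 13.1), so a code opened at the site could reach the assessors.

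As a matter of judgement, an SRG that expects removals to follow may also hesitate to ask for codes when safety calls for them.

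**Working it through.** No arithmetic decides this point, and the plan gives no figure to reproduce. The check sets the three sources side by side and then follows an SRG request through them.

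| Feature | Appendix 2 (SRG request) | Section 10.9.2 | Section 6.3 and SAP 2.4 |
|---|---|---|---|
| Trigger | Masked Cohort 2 review is not enough | Medical emergency or SAE | Any required unmasking |
| Level | Not stated | One subject at a time | Not stated |
| Recipients | The SRG, members not specified | Investigator, Sponsor, other conduct personnel | Two sponsor roles outside study conduct; investigator in an emergency |
| Decision | The SRG's need | Medical Monitor and Sponsor approve; Sponsor is final | Investigator and medical monitor jointly, unless safety or time prevents it |
| Effect on insert | Not stated | Immediate removal | Not stated |

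1. **Is there another route?** No. Section 6.3 says who may see unmasked data. It does not say how an SRG request is met or what happens to the insert. Appendix 2 cites only Section 10.9.2.
2. **Does the medical-need limit in Section 10.9.2 apply to the SRG?** There are two readings, and the reference fails on both.
   - If the limit applies, codes open only for subjects with an emergency, an SAE or another medical need. The remaining assignments stay closed, and Appendix 2 cannot deliver what it promises.
   - If Appendix 2 sets the limit aside, codes open for subjects with no individual medical reason. The unqualified last sentence then calls for removal of their inserts.
3. **Would the site learn the assignment?** It could. The only code-breaking step described is taken by the investigator or designee. That step follows a request that the text attributes to the investigator, and the section also lets codes go to the Sponsor. Site involvement is possible, not certain.
4. **Who has something to lose?** Only subjects with an insert still in place. By design, Formulation 1 lasts 2 to 3 months, Formulations 2A and 2B last 3 to 4 months, and Formulation 3 lasts about 1 week. The planned arms with long-lasting inserts hold 40 + 40 + 40 = 120 of the 140 Cohort 2 subjects, and the short-lived arm holds 20. The 120 is a rough ceiling that would need every code to be opened while those inserts remain. It is not a forecast.
5. **Would grouped tables avoid the problem?** Yes, if they reveal no individual assignment, because the removal sentence turns on a subject's assignment being unmasked. Appendix 2 does not say that the information will come in that form.

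**The case against.** The strongest reply is that the sections should be read together. Section 6.3 governs access whenever unmasking is required, SAP Section 2.4 repeats it, and SAP Section 5 gives the SAP precedence where the two documents differ. Appendix 2 cites Section 10.9.2 for procedure only and does not displace the access rule. This largely stands for access. A reader might infer that following Appendix 2 necessarily unmasks sites, but the documents do not support that: Section 10.9.2 permits release to the Sponsor, and its IRT step carries out an investigator's request, which an SRG review does not contain.

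The reply does not reach the removal rule. Neither Section 6.3 nor SAP Section 2.4 mentions inserts, so reading them alongside Section 10.9.2 leaves its last sentence unqualified. The medical-need limit is no answer either, since applying it leaves the SRG without the data.

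A reader might also infer that SRG membership contradicts Section 6.3, because Section 6.1 and Appendix 2 do not list the Sponsor Statistician and do list roles without access. That is not supported. Section 6.1 sets only a minimum membership, the Appendix 2 list is tied to the decision to open Cohort 2, and a two-person limit necessarily leaves other members out.

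Two further objections are fair. Masked review is the default, so the route may never be used. Restricting data to two people also affects how a group that seeks consensus works, although Section 6.3 already implies that restriction.

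**Conclusion.** The point holds as a faulty cross-reference combined with an unqualified removal rule. Section 10.9.2 is the wrong procedure for an SRG request. Taken literally, it either withholds the data or calls for removal of inserts that cannot be replaced, in subjects with no medical reason of their own. Conflict with restricted access is a possibility, not a necessary result.

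The likelihood is low and cannot be estimated from the documents. Three things must coincide: masked review proves insufficient, individual codes are opened, and an insert is still in place. The consequence also assumes that staff apply the last sentence of Section 10.9.2 as written. A reader might infer bias in the Week 12 Schirmer comparison. The documents do not support that, because they give no basis for how often the SRG would ask or how many codes would be opened.

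The correction is worth making because the text concerns safety and masking, the harm to an affected subject cannot be undone within the study, and the remedy is small.

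**What to change.** 1. **Appendix 2.** Replace the reference to Section 10.9.2 with: *Unmasked Cohort 2 information will be supplied only to the individuals named in Section 6.3, without a site IRT code break; such unmasking does not by itself require insert removal.*
2. **Section 10.9.2.** End the removal sentence with *unmasked under this section*. The rule stays in force for medical emergencies and SAEs.
3. **Section 6.3.** State that the joint decision by the Investigator and medical monitor applies to subject-level unmasking and not to SRG requests. Otherwise an SRG request would still pass through an investigator. Make the same change in SAP Section 2.4, which repeats that sentence.

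Naming the Sponsor Statistician in the SRG membership in Section 6.1 and Appendix 2 would be an optional consistency edit.

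The cost is one replaced sentence, three added words and one clarifying clause in each document. Sample size, endpoints, visits and analyses do not change. In practice, the two named individuals need the data supplied outside the site's IRT function. The downside is that SRG members not named in Section 6.3, including Principal Investigators and the Chief Medical Officer, must rely on the two who are. Section 6.3 already implies this.
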